10.3. Demographic and Baseline Characteristics

A summary of demographics and baseline information will be presented for each treatment group and for all subjects for the ITT population.

The demographic characteristics consist of age at randomization (years), sex, race, ethnicity, geographic ancestry and fertility status. A subject's age in years is calculated as (randomization date – date of birth)/365.25. A subject's race is determined as described in Section 9.2.2.

The baseline characteristics consist of baseline height (cm), baseline weight (kg), baseline body mass index (BMI) (kg/m²), disease duration, and baseline prednisone dose. Body mass index, calculated as (body weight in kilograms) / (height in meters)² is collected in the eCRF.

Age at randomization (years), baseline height (cm), baseline weight (kg), and baseline BMI (kg/m²) will be summarized using descriptive statistics. The number and percentage of subjects by age category (<65, ≥65 years) and (<Median, ≥Median), sex (Male, Female), ethnicity (Hispanic or Latino, Not Hispanic or Latino), disease duration (≤1 year, >1 year), and baseline prednisone dose (<60 mg, ≥60 mg) will also be reported. Percentages will be based on the total number of subjects in the population being summarized.

Subject demographic and baseline characteristics, including geographic ancestry (from which race is derived), will be presented in a listing for all subjects in the population

being summarized. The number and percentage of subjects for each collected race category will be presented along with the demographic characteristics for each treatment group and for all subjects for the population being summarized.

A summary of substance (tobacco) use (both categorical and quantitative), collected at Screening, will be presented as well as a by-subject listing of data on tobacco use for all subjects in the ITT population. A subject's smoking pack-years is calculated as (number of cigarettes smoked per day/20) * (number of years smoked).

Smoking status updates reported at Baseline, Week 24 and Week 60/Early Withdrawal will be summarized by visit for all subjects in the ITT population and will be presented in a data listing.

For subjects who experience a liver event, alcohol use (categorical) and the volume of consumption (quantitative) will be summarized and presented in a data listing with the liver event data for the ITT population. In the United States (US): 1 unit of alcohol = 1.5 oz hard liquor, 1 beer, 4 oz wine (or metric equivalent). In the United Kingdom (UK): 1 unit of alcohol = 1 measure of spirits, 1/2 pint beer, 1 small glass of wine (125mL) (or metric equivalent).

10.4. Concomitant Medications

Subjects may take other medications for treatment of the symptoms associated with PV, so long as they do not fall into any of the prohibited medications categories specified in the protocol.

Concomitant medications terms will be coded using an internal validated medication dictionary, GSKDrug and will be reported by Anatomical Therapeutic Chemical (ATC) class and medication. GSKDrug Version 1.2 or higher, that covers all approved drugs in studies where Japan is participating, will be referenced.

As discussed in Section 9.3.2, all medications will be assigned to a therapy period and a medication will be counted in each period during which it is used.

All concomitant medications will be presented in a data listing for the ITT population. This listing will indicate in which study period(s) the concomitant medications were taken. A separate data listing will be provided for use of steroids medications only.

10.5. Acetaminophen and Antihistamine Use

As noted above, medication terms will be coded using an internal validated medication dictionary, GSKDrug. Pre-dose acetaminophen and antihistamine use is specifically noted in the eCRF. Post-dose use subsequent to the baseline visit that is not administered at the study site is collected in the eCRF with all other concomitant medications. Post-dose use at the baseline visit that is administered at the study site will be listed for the ITT population.

Pre-dose acetaminophen and antihistamine use will be presented in a data listing for the ITT population.

10.6. Steroid Taper

Subjects will remain on the stable daily oral steroid dose achieved during the Screening Period until Week 2, when they will begin tapering their steroid dose with the goal of reducing or eliminating the daily use of steroids. Subjects' daily oral steroid dose will be reduced by 1 dose level every 2 weeks until the onset of disease flare/relapse. For a subject who experiences disease flare/relapse, the prednisone/prednisolone dose will be increased by 1 to 4 levels per week until disease control is achieved (i.e, no new lesions for ≥ 2 weeks); the prednisone/prednisolone taper will then be reinitiated after a 2-week period of disease control.

Table 10-2 Oral Prednisone/Prednisolone Dose-taper Schedule

Current Dose	Next Taper Dose ^a (every 2 weeks)	Increase Dose for Flare/Relapse ^b (increase by 1 to 4 levels per week)				Dose for Post-Flare Taper
		1 level	2 levels	3 levels	4 levels	
160	140	180	200	220	240	Decrease dose by 1 level after 2 weeks of disease control, then return to standard taper schedule.
140	120	160	180	200	220	
120	100	140	160	180	200	
100	80	120	140	160	180	
80	60	100	120	140	160	
60	50	80	100	120	140	
50	40	60	80	100	120	
40	30	50	60	80	100	
30	25	40	50	60	80	
25	20	30	40	50	60	
20	17.5	25	30	40	50	
17.5	15	20	25	30	40	
15	12.5	17.5	20	25	30	
12.5	10 ^c	15	17.5	20	25	
10 ^c	7.5	12.5	15	17.5	20	
7.5	5	10 ^c	12.5	15	17.5	
5	2.5	7.5	10 ^c	12.5	15	
2.5	0	5	7.5	10 ^c	12.5	
0	0	2.5	5	7.5	10 ^c	

- Prednisone/prednisolone is reduced by 1 dose level every 2 weeks, with the goal being elimination of prednisone/prednisolone. For subjects at a starting dose >160 mg, taper dose by 20 mg every 2 weeks until the dose is 160 mg, at which point the decrements shown on the table above should be used.
- Subjects will remain on the standardized oral prednisone/prednisolone taper schedule until disease flare/relapse. In the event of disease flare/relapse, oral prednisone/prednisolone will be increased by a rate of 1 to 4 levels per week until disease control is re-established. The oral prednisone/prednisolone taper will then be reinitiated after disease control is maintained for 2 weeks.
- Once the dose is reduced to 10 mg, an attempt at reducing the steroid dose further need only be attempted until the first flare/relapse occurs. In the event of a flare/relapse at a prednisone/prednisolone dose of ≤10 mg/day, the dose will be temporarily increased in order to reestablish disease control (no new lesions for >2 weeks); after disease control is maintained, further steroid tapering attempts to <10 mg will be at the investigator's discretion.

A steroid administration log capturing the tapering of the medication will be collected in the eCRF.

A by-visit summary of oral prednisone/prednisolone dose and a summary of each subject's cumulative oral prednisone/prednisolone dose will be presented using descriptive statistics for each treatment group. Additionally, since a subject's steroid dose at each visit is dependent upon his/her stable dose achieved during Screening, descriptive statistics will be presented for the oral prednisone/prednisolone dose at each visit for each stable dose level of oral prednisone/prednisolone achieved during Screening for each treatment group.

Tables summarizing oral prednisone/prednisolone dose will be presented for the ITT population.

The information collected in the steroid taper log will be presented in a data listing for the ITT population.

10.7. Medical History

Any significant medical conditions affecting the subject in the past 5 years and whether the condition occurred in the past or is a current condition will be recorded in the eCRF.

Medical history information will be presented in a data listing for the ITT population.

10.8. Pemphigus Vulgaris History

Details of the subject's PV history will be collected in the eCRF. The time (in years) since PV symptom onset, the time (in years) since PV diagnosis, the number of flares/relapses since diagnosis and the time (in years) since the subject's most recent failed steroid taper that resulted in a disease flare/relapse at a prednisone/prednisolone dose >10 mg/day will be summarized using descriptive statistics for each treatment group for the ITT population. The time since PV symptom onset and PV diagnosis are defined in Section 9.2.3. The time since the most recent failed steroid taper is defined in Section 9.2.4.

PV history information will be presented in a data listing for the ITT population.

11. EFFICACY ANALYSES

Baseline prednisone/prednisolone dose and disease duration will be used to stratify all primary and secondary analyses.

Summary statistics will be provided for the primary and key secondary variables

As noted in Section 8.2, covariate analyses will be performed on the co-primary efficacy endpoints:

- Proportion of subjects achieving remission on minimal steroid therapy at Week 60.
- Time to remission while on minimal steroid therapy by Week 60.
- Time to initial flare/relapse by Week 60.
- Proportion of subjects who did not flare/relapse by Week 60. A flare/relapse is defined as new lesions that do not heal spontaneously within 1 week, or when there is an extension of lesions that were present at the randomization visit.

The primary analysis for the co-primary endpoints will use the ITT population. The ITT population will also be used for all secondary and other efficacy analyses.

If the PP population comprises between 50% and 95%, inclusive, of the ITT population, it will be used for a confirmatory analysis of the co-primary endpoints and the key secondary efficacy endpoints identified above.

The primary efficacy and key secondary efficacy endpoint parameters will be presented in a data listing for the ITT population.

11.1. Primary Efficacy Analyses

11.1.1. Time to SR on Minimal Steroid Therapy by Week 60

The co-primary efficacy endpoint of time to SR on minimal steroid therapy by Week 60 (as defined in Section [2.2.1](#)) will be analyzed using a log-rank test stratified by baseline prednisone/prednisolone dose and disease duration strata. Subjects who discontinue prematurely (prior to Week 60) and who have not achieved remission upon discontinuation will be censored at the time they discontinued. Subjects who reach Week 60 without remission will be censored at the date of their last visit.

For subjects achieving remission, time to SR on minimal steroid therapy will be derived as: [(the date on which the subject initially tapered his/her oral prednisone/prednisolone dose to ≤ 10 mg/day and maintained ≤ 10 mg/day of oral prednisone/prednisolone with no new or nonhealing (established) lesions for ≥ 8 weeks and maintained that status until Week 60) – (the date of randomization)] + 1 day.

A summary table presenting the Kaplan-Meier estimates for the time to SR and 95% CI at Week 4, week 8, Week 12 etc. for each of the treatment groups and p-value for the treatment difference, using the 2-sided log-rank test indicated above will be presented for the ITT population and PP population (if criteria are met as discussed in Section [11](#)).

For the covariate analysis, a summary table computing hazard ratio and 95% CI for the hazard ratio and the p-value using the Cox proportional hazards model discussed in Section [8.2](#), will be presented for the full model for the ITT population.

A Kaplan-Meier plot of time to SR on minimal steroid therapy will be constructed for each treatment group for the ITT population.

11.1.2. Duration of Remission on Minimal Steroid Therapy by Week 60

The co-primary endpoint of duration of remission on minimal steroid therapy will be analyzed using a rank ANCOVA [[Stokes 2000](#)], with treatment as a main effect, and baseline prednisone/prednisolone dose and disease duration strata as covariates. If a subject discontinues the study prior to Week 60, the subject will be considered as not in remission from the date of the last known study visit until Week 60.

For subjects who complete the study without experiencing any periods of remission, duration of remission on minimal steroid therapy will be 0 days.

One Period of Remission

For subjects who experience one period of remission on minimal steroid therapy that:

- Is continuing at the Week 60 study visit (or early discontinuation):

- Duration of remission on minimal steroid therapy will be derived as: [(the date of the Week 60 study visit/date of last known visit) - (the date on which an absence of new or nonhealing lesions occurs while the subject is on a prednisone/prednisolone dose of ≤ 10 mg/day for ≥ 8 weeks)] + 1 day.
- Relapses/flare prior to the Week 60 study visit (or early discontinuation):
 - Duration of remission on minimal steroid therapy will be derived as: [(the date on which flare/relapse occurs) - (the date on which an absence of new or nonhealing lesions is found while the subject is on a prednisone/prednisolone dose of ≤ 10 mg/day for ≥ 8 weeks)].

Note that for periods of remission that end with relapse/flare, “+ 1 day” is not included in the calculation since the end date is the date on which relapse/flare occurs so the subject is not considered to be in remission on that day.

More Than One Period of Remission

For subjects who experience more than one period of remission on minimal steroid therapy (i.e. a subject went into remission, then relapsed, and then went into remission again (or possibly more than 2 episodes of remission)) the duration of remission will be the sum of all periods of remission while on minimal steroid therapy up to Week 60.

Individual periods of remission will be defined as specified above for subjects experiencing one period of remission. Duration of remission will be derived as the sum of all individual periods of remission.

A summary table computing the raw duration and p-value for the treatment difference, using the rank ANCOVA indicated above, will be presented for the ITT population and PP population (if criteria are met as discussed in Section [11](#)).

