8.2. Study Design Considerations

8.2.1. Sample Size Assumptions

Assuming that the proportion of subjects achieving SR on minimal steroid therapy status is 54% and 80% in the placebo and the ofatumumab SC groups, respectively [Beissert, 2010], with proportional hazards across the various strata, a sample size of 68 subjects per group will give $\geq 90\%$ power for a statistically significant difference between the two groups in time to SR on minimal steroid therapy, using a two-sided 0.05 level of significance. Note that for the purpose of sample size calculation of time to SR, “survival” means: “Not in SR”, and hence $(100-54=)$ 46%, and $(100-80=)$ 20% are the survival rates for the placebo and ofatumumab SC treatment groups respectively needed to calculate sample size for the log-rank test. The study is designed to detect a hazard ratio of 0.48248 (median time to response on ofatumumab SC/median time to response on placebo). It is assumed that no more than 13% of the subjects in both groups will be lost to follow-up before their Week 60 visit. With the projected 54% and 80% SR rates in the placebo and active groups respectively, a total of approximately 80 subjects with SR in both treatment groups combined are needed at the end of the study. Because this study has 2 co-primary efficacy endpoints, an evaluation of the overall power to detect at least one significant endpoint was made using simulations. The analysis proposed for the

co-primary endpoints is a sequential test based on the method of Alosch and Huque [Alosch, 2010]. Results of the simulations are displayed in Table 8-2.

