8.2. Other Strata and Covariates

The study randomization is stratified by disease duration [≤ 1 year, > 1 year] and baseline prednisone dose [< 60 mg, ≥ 60 mg].

The randomization strata of disease duration and baseline prednisone dose will be included in the base model for the analysis of the co-primary efficacy endpoints. Due to smaller sample size in the analysis, we will remove one or both strata from the analysis model if the model does not converge.

In addition to the co-primary endpoints, baseline prednisone/prednisolone dose and disease duration will be used to stratify all secondary efficacy analyses.

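### The visible efficacy models use starting prednisone dose only as below or at least 60 mg, leaving taper-driven variation unadjusted; adding the exact dose gives a small gain for duration of remission and a larger one for cumulative steroid dose

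*SAP*

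**What the plan says.** For the co-primary duration endpoint, SAP Section 11.1.2 specifies a rank ANCOVA "with treatment as a main effect, and baseline prednisone/prednisolone dose and disease duration strata as covariates". Read alone, this could mean dose in mg plus a duration stratum. SAP Section 8.2 settles the reading for the co-primary endpoints: "The randomization strata of disease duration and baseline prednisone dose will be included in the base model". SAP Sections 3.1 and 7.2 define the dose stratum as below 60 mg or at least 60 mg.

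For continuous secondary endpoints, Protocol Section 8.3.6.5 gives a general rule: ANCOVA with treatment and the strata, plus the baseline value only when the endpoint is a change from baseline. Cumulative corticosteroid dose is a secondary endpoint and is not a change from baseline.

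The taper starts at Week 2 and drops one level every two weeks until flare (Protocol Table 3-2, SAP Table 10-2). SAP Section 10.6 recognises the consequence, stating that a subject's "steroid dose at each visit is dependent upon his/her stable dose achieved during Screening", and plans descriptive summaries by each stable Screening dose. No visible efficacy model includes the exact dose.

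**The concern.** Remission on minimal steroid therapy cannot begin before a subject is at 10 mg/day or less. Under a fixed taper, the earliest possible date is set at baseline by the starting dose. Two subjects in the same stratum can differ by weeks in the longest remission they could achieve, whatever their treatment, and by a factor of two or more in scheduled cumulative dose. The two-level stratum removes only part of this, and the rest is treated as noise.

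The stratum also leaves exact dose within strata to chance balance. With 69 subjects randomized (SAP Sections 1 and 5) instead of the planned 136, both matter more than they would have at full size. Adjusting for a baseline value that is already collected is routine.

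**Working it through.** **The plan's own figure.** Inputs from Protocol Section 8.2.1: "achieving SR on minimal steroid therapy status is 54% and 80% in the placebo and the ofatumumab SC groups"; "The study is designed to detect a hazard ratio of 0.48248"; "using a two-sided 0.05 level of significance"; "a total of approximately 80 subjects with SR in both treatment groups combined are needed"; and "a sample size of 68 subjects per group will give" at least 90% power.
- Hazard ratio: ln(0.46)/ln(0.20) = 0.48248.
- Events (Schoenfeld): 4(1.960 + 1.282)²/(ln 0.48248)² = 79.1, taken as 80. Power at 80 events is 90.3%.
- Subjects: 80/0.67 = 119.4, or about 59 evaluable per group after rounding down; 59/0.87 = 67.8, so 68 per group.

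The stated sample size reproduces, and this point does not affect it.

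**Taper without flare** (Table 3-2). Earliest week at 10 mg = 2 × number of levels from start to 10 mg. Cumulative dose = 14 days × the sum of the levels from start down to 2.5 mg.

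| Start (mg/day) | Week at 10 mg | Most weeks at ≤10 mg by Week 60 | Cumulative dose (mg) |
|---|---|---|---|
| 20 | 8 | 52 | 1260 |
| 25 | 10 | 50 | 1610 |
| 30 | 12 | 48 | 2030 |
| 40 | 14 | 46 | 2590 |
| 50 | 16 | 44 | 3290 |
| 60 | 18 | 42 | 4130 |
| 80 | 20 | 40 | 5250 |
| 100 | 22 | 38 | 6650 |
| 120 | 24 | 36 | 8330 |

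For example, from 20 mg: 14 × (20 + 17.5 + 15 + 12.5 + 10 + 7.5 + 5 + 2.5) = 14 × 90 = 1260. The spread inside the strata is 16 − 8 = 8 weeks below 60 mg and 24 − 18 = 6 weeks at or above it. Cumulative dose spans 1260 to 3290 mg and 4130 to 8330 mg.

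**How much the stratum already captures.** Assume equal use of the nine levels. The week at 10 mg has mean 16 and variance 26.7. The stratum means are 12 (five levels) and 21 (four levels), so the between-stratum variance is (5 × 4² + 4 × 5²)/9 = 20, a share of 20/26.7 = 75%. Across three assumed dose distributions the share is 62 to 75%, counting both the week at 10 mg and cumulative dose. So 25 to 38% of the taper-driven variance is unused.

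**What survives flares and dropout.** A weekly simulation set flare rates to give 54% and 80% sustained remission, with 13% dropout. It compared residual variance under treatment plus stratum with treatment plus stratum plus exact level. Flare process and dose distribution are assumptions.
- Ranked duration, equal use of levels, flare raising dose by 1, 2 or 4 levels, with or without between-subject variation in flare rate: reduction of 3.7 to 5.9%. Other calibrated runs gave 4.3 to 8.0%; one distribution skewed to high doses gave 3.2%.
- Power for duration at 69 subjects, three dose distributions: 74.9 to 75.8%, 75.1 to 76.6% and 74.8 to 75.6%. At 136 subjects the gain is below 0.5 point.
- If half the subjects are assumed cut short between Weeks 4 and 60: reduction of about 1.5 to 3%.
- Cumulative dose: about 1.5 to 35% on the raw scale and 14 to 59% on ranks.

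**Chance imbalance at 69 subjects.** Assume half the subjects in each stratum, equal use of levels and 1:1 allocation. The within-stratum variances of the week at 10 mg are 8 and 5, average 6.5. The between-arm difference in means has SD √(6.5 × 4/69) = 0.61 week, so a gap above 1.2 weeks arises about 5% of the time. Flares would dilute its effect on the endpoint.

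**The case against.** The case against is substantial, and much of it stands.

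**Adjusting for the strata is not an error.** It is the protocol's specified analysis, it gives a valid test, and the stratum captures most of the taper effect. This stands: the point concerns precision only.

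**The gain is small for duration and not free.** A reader might infer from 6 to 8 weeks of unadjusted spread that precision would improve greatly. The documents do not support that, because flares and dropout dominate the endpoint. One more covariate at 69 subjects costs about 1/65 = 1.5% of precision. If termination cut many subjects short, the net gain for duration could be close to zero. The documents do not say how many were affected.

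**Timing.** The SAP is dated 29 March 2018. The Amendment 7 rationale in Protocol Appendix 15 says the sponsor unblinded assignments after termination, while SAP Section 3.1 places unblinding at database freeze. Whether the analysis team knew the codes is unclear. This stands, and it limits how the adjusted model can be presented.

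**Simplification.** The SAP reduces its analyses because of the small sample and allows strata to be dropped if a model does not converge. That argues against elaborate models, but one covariate in a rank ANCOVA is a small addition.

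Three broader readings are tempting and not supported:
- That exact dose is ignored throughout. SAP Section 10.6 uses it descriptively, by treatment.
- That the Cox models also omit it. SAP Sections 11.1.1 and 11.2.3 refer to a full model whose covariates are not listed.
- That the SAP gives cumulative dose no suitable model. The efficacy text after Section 11.2.3 is not visible, so only the protocol's general rule can be cited.

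**Conclusion.** The point holds for the visible inferential models, as a modest loss of precision. The within-stratum spread of 8 and 6 weeks, and the cumulative-dose ranges, follow exactly from the taper table and need no assumption beyond the absence of flare.

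The statistical gain does rest on assumptions about flare rates, starting doses and early stopping. For ranked duration it is roughly 4 to 8% of residual variance when calibrated to the protocol's remission rates, about 1 to 1.5 power points at 69 subjects (0.7 in the least favourable run), and 1.5 to 3% if many subjects were cut short. The benefit is clearer for cumulative dose, especially on ranks, provided the protocol's strata-only rule is what is applied. The calibrated runs agree on direction before the degree-of-freedom cost; the size is uncertain. The co-primary stratified log-rank test for time to sustained remission is untouched.

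**What to change.** Keep the randomization strata. In SAP Sections 8.2 and 11.1.2, add exact baseline prednisone/prednisolone dose, as taper level or ranked mg/day, as a covariate in the rank ANCOVA for duration of remission. Do the same in the ANCOVA for cumulative corticosteroid dose. Reword Section 11.1.2 so that the dose adjustment is explicitly the stratum plus exact dose.

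State whether the analysis team had access to treatment codes when the covariate was chosen. If it did, keep the protocol model as the main analysis and report the adjusted one beside it as a supplementary analysis declared before it is run.

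The cost is one model degree of freedom, a short SAP change and a documented departure from the protocol's covariate set. No new data are needed, since steroid dose is recorded at Baseline and at every visit.
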